Table 4: Planned Collection of PRESORS ClinRO, PRESORS ObsRO and Clinical Evaluation

Assessments	Cohort 1		Cohort 2
	During Hospitalization	After Discharge	
PRESORS ClinRO	BID from Day 1 to Day 14 and QD from Day 15 to Day 21	Once at clinic visits	Once at clinic visits
Clinical Evaluation^f/ SBP+DBP	BID from Day 1 to Day 21 + Day 28*	Once at clinic visits + Day 28*	Once at clinic visits + Day 28*
PRESORS ObsRO	BID from Day 1 to Day 14 and QD from Day 15 to Day 21		
Body Temp Caregiver	NA	BID from Day 2 to Day 14 and QD from Day 15 to Day 21	BID from Day 1 to Day 14 and QD from Day 15 to Day 21

^f Clinical evaluation includes respiratory rate, heart rate, body temperature, and SpO2.

* Only in case of on-site visit.

Visit windows for these assessments are defined as in **Table 5**.

Table 5: Visit Windows for PRESORS ClinRO, PRESORS ObsRO, Clinical Evaluation (including SBP/DBP) and Body Temperature

Analysis Time	Time Interval	Target Time
Baseline		0
12h (Day 1.5)	>0h [§] ; 17h59min	12h
24h (Day 2.0)	18h; 29h 59 min	24h
36h (Day 2.5)	30h; 41h 59min	36h
48h (Day 3.0)	42h; 53h 59min	48h
60h (Day 3.5)	54h; 65h 59min	60h
72h (Day 4.0)	66h; 77h 59min	72h
84h (Day 4.5)	78h; 89h 59min	84h
96h (Day 5.0)	90h; 101h 59min	96h
108h (Day 5.5)	102h; 113h 59min	108h
120h (Day 6.0)	114h; 125h 59min	120h
132h (Day 6.5)	126h; 137h 59min	132h
144h (Day 7.0)	138h; 149h 59min	144h
156h (Day 7.5)	150h; 161h 59min	156h
168h (Day 8.0)	162h; 173h 59min	168h
180h (Day 8.5)	174h; 185h 59min	180h
192h (Day 9.0)	186h; 197h 59min	192h
204h (Day 9.5)	198h; 209h 59min	204h
216h (Day 10.0)	210h; 221h 59min	216h
228h (Day 10.5)	222h; 233h 59 min	228h
240h (Day 11.0)	234h; 245h 59min	240h
252h (Day 11.5)	246h; 257h 59min	252h
264h (Day 12.0)	258h; 269h 59min	264h
276h (Day 12.5)	270h; 281h 59min	276h
288h (Day 13.0)	282h; 293h 59 min	288h

Table 5: Visit Windows for PRESORS ClinRO, PRESORS ObsRO, Clinical Evaluation (including SBP/DBP) and Body Temperature

Analysis Time	Time Interval	Target Time
300h (Day 13.5)	294h; 305h 59min	300h
312h (Day 14.0)	306h; 317h 59min	312h
Day 15	Day [15] (2 AM-1:59 AM)	15
Day 16	Day [16] (2 AM-1:59 AM)	16
Day 17	Day [17] (2 AM-1:59 AM)	17
Day 18	Day [18] (2 AM-1:59 AM)	18
Day 19	Day [19] (2 AM-1:59 AM)	19
Day 20	Day [20] (2 AM-1:59 AM)	20
Day 21	Day [21] (2 AM-1:59 AM)	21
Day 22	Day [22] (2 AM-1:59 AM)	22
Day 23	Day [23] (2 AM-1:59 AM)	23
Day 24	Day [24] (2 AM-1:59 AM)	24
Day 28	Day [25, $+\infty$] (2 AM-1:59 AM)	28

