Duration of supplemental hydration/feeding (hours) [duration]	Total number of hours of hydration/feeding support experienced from first dose of study drug until end of study (sum of the duration of individual hydration/feeding administration records captured in the Feeding/Supplemental Feeding eCRF) and is derived as: $\text{time hours} = \text{sum} [(\text{end date/time} - \text{start date/time}) \text{ [of encounter]}] / 3600$ Derivation and imputation rules: as for 'Duration of need for intensive care unit (ICU) stay (hours)'
Time (hours) to end of oxygen supplementation up to 72h from first hospital discharge [time to event]	Regardless of whether or not the subject is receiving oxygen supplementation at time of first dose of study drug: time (hours) from first dose of study drug to last end date/time of any oxygen supplementation received, but within 72h following first hospital discharge. Excludes oxygen supplementation received during re-hospitalizations that occurred >72 hours after initial hospital discharge Time (hours) will be set to 0h for subjects not requiring oxygen supplementation after first dose of study drug. Censoring will be applied as follows:

Situation**Censoring**

Table 20: Additional Clinical Course Parameters for Hospitalized Subjects

	
For subjects with missing data prior to event due to:
 
 • Completion • Withdrawal/early discontinuation of the study • Lost to follow-up (LTFU) 
Death (without previous evidence of supplementation end/hospital discharge)
	
Censored at date/time of completion, withdrawal/discontinuation of the study or LTFU accordingly Note: missing time will be imputed as 12:00
 
Censored at date/time of death
				
		time to event (hours) = (date/time of event or censoring – date/time of first dose of study drug)/3600, rounded to one decimal				

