Time (hours) to end of hydration/feeding supplementation up to 72h from first hospital discharge [time to event]	
Regardless of whether or not the subject is receiving hydration/feeding supplementation at time of first dose of study drug: time (hours) from first dose of study drug to last end date/time of any hydration/feeding supplementation received, but within 72h following first hospital discharge. Excludes hydration/feeding supplementation received during re-hospitalizations that occurred >72 hours after initial hospital discharge
 
Time (hours) will be set to 0h for subjects not requiring hydration/feeding supplementation after first dose of study drug.
 
Censoring will be applied as follows:
	
Situation
 
 
 For subjects with missing data prior to event due to:	Censored at date/time of completion, withdrawal/discontinuation of the study or LTFU accordingly Note: missing time will be imputed as 12:00	
 
 Death (without previous evidence of supplementation end/hospital discharge)	Censored at date/time of death	
 
 
time to event (hours) = (date/time of event or censoring – date/time of first dose of study drug)/3600, rounded to one decimal
	For subjects with missing data prior to event due to:	Censored at date/time of completion, withdrawal/discontinuation of the study or LTFU accordingly Note: missing time will be imputed as 12:00	Death (without previous evidence of supplementation end/hospital discharge)	Censored at date/time of death
For subjects with missing data prior to event due to:	Censored at date/time of completion, withdrawal/discontinuation of the study or LTFU accordingly Note: missing time will be imputed as 12:00					
Death (without previous evidence of supplementation end/hospital discharge)	Censored at date/time of death					

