Time (hours) to end of supplementation (oxygen and/or feeding/hydration) up to 72h from first hospital discharge [time to event]	
Time (hours) from first dose of study drug until the maximum date/time of supplementation end (oxygen- and/or hydration/feeding) and excluding supplementation received during re-hospitalizations that occurred >72 hours after initial hospital discharge.
 
Time (hours) will be set to 0h for subjects not requiring supplementation (oxygen- and/or hydration/feeding) after first dose of study drug.
 
In case either of the two components are censored, the time to actual end of supplementation (oxygen and/or hydration/feeding)
					

Table 20: Additional Clinical Course Parameters for Hospitalized Subjects

	
will also be censored at the last timepoint of the censored component.
 
time to event (hours) = (maximum (date/time of event or censoring) – date/time of first dose of study drug)/3600, rounded to one decimal

Time (hours) to return to pre-RSV disease level for RR: based on investigator evaluation [time to event]
	
The time (hours) from first dose of study drug until the date/time to return to pre-RSV disease level. The return to pre-RSV disease level occurs when the observed value of the parameter is indicated by the investigator as normal, and no later observed values are indicated by the investigator as abnormal (=event).
 
Normalization of RR will be derived from the investigator response to the corresponding question in the Vital Signs eCRF: 'Is this RR value normal for this patient?'
 
If no deterioration from pre-RSV disease levels occurred, the time will be set to time of first dose of study drug and the value will be set to 0 hours.
 
Subjects with an abnormal value at the last assessment will be censored at that time. Subjects for which this last assessment is the baseline assessment will be censored at time 0 hours.
 
time to event (hours) = (date/time of event or censoring – date/time of first dose of study drug)/3600, rounded to one decimal

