
Time (hours) to return to pre-RSV disease level for HR: based on investigator evaluation [time to event]
	
Censoring rules and derivation: as for 'Time to return to pre-RSV disease level for RR: based on investigator evaluation'
 
Normalization of HR will be derived from the investigator response to the corresponding question in the Vital Signs eCRF: 'Is this Pulse value normal for this patient?'

Time (hours) to SpO₂ ≥ 92% on room air [time to event]
	
The time from first dose of study drug until the time of first SpO₂ measurement ≥ 92% on room air, and where no supplemental oxygen supplementation is given at or after this timepoint and where no value < 92% are measured after this timepoint.
 
Subjects with SpO₂<92% on room air or who are still on oxygen supplementation at the last SpO₂ assessment will be censored at the date and time of the last SpO₂ assessment.
 
If no oxygen supplementation was necessary post-baseline and the subject had SpO₂ measurement ≥ 92% on room air at baseline and all post-baseline measurements, the value (time to event [hours]) will be set to 0 hours.
 
If the subject required supplemental oxygen prior to the current respiratory infection, end date/time will be defined as the date/time the subject has returned to the level provided prior to the current respiratory infection.
 
time to event (hours) = (date/time of event or censoring – date/time of first dose of study drug)/3600, rounded to one decimal

Table 20: Additional Clinical Course Parameters for Hospitalized Subjects

Time (hours) to $\text{SpO}_2 \geq 95\%$ on room air [time to event]	Censoring rules and derivation: as for 'Time (hours) to $\text{SpO}_2 \geq 92\%$ on room air'

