	
 Normalization of oxygen supplementation (as in parameter Time [hours] to end of oxygen supplementation up to 72h from first hospital discharge), Normalization of feeding/hydration (as in parameter Time [hours] to end of hydration/feeding supplementation up to 72h from first hospital discharge), Normalization of RR (as in parameter Time [hours] to return to pre-RSV disease level for RR: based on investigator evaluation), and Normalization of HR (as in parameter Time [hours] to return to pre-RSV disease level for HR: based on investigator evaluation), and Normalization of blood oxygen level (as in parameter Time [hours] to $\text{SpO}_2 \geq 95\%$ on room air) 
In case any of the five components are censored, the time to clinical stability (protocol definition) will also be censored at the last timepoint of the censored component.
 
time to event (hours) = (maximum (date/time of event criteria or censoring) – date/time of first dose of study drug)/3600, rounded to one decimal

Need for re-hospitalization [categorical]	
If, after being discharged from the hospital (initial hospital discharge), subject is re-hospitalized (ward or ICU [inpatient status]) due to respiratory or other reasons. Re-hospitalization status will be categorized as:
 
 Yes 
 Hospital admission date/time at least 24 hours after initial hospital discharge date/time AND Reason for re-hospitalization, as assessed by the investigator, indicated on Medical Encounters [Inpatient/Outpatient] eCRF as: 
 AE Other 
If reason for re-hospitalization is indicated as AE, further differentiation will be made as follows:
 
 Respiratory AEs: 
 RSV-related complications: modified definition as detailed in Section 5.4 Other respiratory AEs Non-respiratory AEs 
This variable is only derived for those subjects who are re-hospitalized

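### Within time to clinical stability, oxygen given in a late readmission is excluded by the oxygen component but counted again by the SpO2 component

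*SAP*

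**What the plan says.** All the definitions are in Table 20 of SAP Section 5.3.1.3.2.

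- **Oxygen component.** It runs to the "last end date/time of any oxygen supplementation received, but within 72h following first hospital discharge". Table 20 then adds: "Excludes oxygen supplementation received during re-hospitalizations that occurred >72 hours after initial hospital discharge".
- **Feeding/hydration component.** It has the same form, running to the "last end date/time of any hydration/feeding supplementation received, but within 72h following first hospital discharge", with the same exclusion of late readmissions.
- **SpO2 component.** It is the first reading at or above the threshold on room air, "where no supplemental oxygen supplementation is given at or after this timepoint and where no value < 92% are measured after this timepoint". The 95% version follows the same rules. Neither has a time limit or a readmission exclusion. A child still on oxygen at the last SpO2 assessment is censored there.
- **RR and HR components.** A reading must be marked normal by the investigator, with the condition that "no later observed values are indicated by the investigator as abnormal (=event"). For a child who ends abnormal, "Subjects with an abnormal value at the last assessment will be censored at that time".
- **Composite.** The five parameters are used unchanged and the time is computed from the "maximum (date/time of event criteria or censoring"). If any component is censored, the composite is censored.

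Nothing else in the SAP extends the late-readmission exclusion to the SpO2, HR or RR components.

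**The concern.** Two rules inside one endpoint treat the same event in opposite ways. The oxygen component says that oxygen given in a readmission starting more than 72 h after first discharge is not part of the recovery being timed. The SpO2 component says that any later oxygen, whenever it is given, cancels the earlier recovery. Under a maximum the later time wins, so the SpO2 rule always overrides the oxygen exclusion.

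A programmer following Table 20 literally would produce an endpoint that ignores late oxygen in name only. For an affected child, the derived time describes the later admission and not the index RSV illness. If the child is still on oxygen at the last SpO2 assessment, an observed recovery becomes a censored one.

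**Working it through.** The SAP states no sample size, power or expected event count for this endpoint, so there is no figure of its own to reproduce. The check applies the Table 20 rules to a single child.

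**Inputs.** Hours from first dose at Day d = (d − 1) × 24, which agrees with Table 5 (Day 14 = 312 h). The child is assumed: all five criteria met by discharge at 48 h, readmitted on Day 16, oxygen until Day 18, room-air SpO2 at or above 95% afterwards, no HR or RR marked abnormal after 48 h.

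- Readmission: (16 − 1) × 24 = 360 h. End of oxygen: (18 − 1) × 24 = 408 h.
- Gap from discharge to readmission: 360 − 48 = 312 h, well beyond 72 h, so the exclusion applies.

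| Component | As written | With the exclusion carried into SpO2 |
|---|---|---|
| Oxygen | at most 48 h | at most 48 h |
| Feeding/hydration | at most 48 h | at most 48 h |
| RR and HR | at most 48 h | at most 48 h |
| SpO2 | at least about 408 h | at most 48 h |
| **Composite (maximum)** | **at least about 408 h** | **at most 48 h** |

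The shift is at least about 408 − 48 = 360 h, or 15 days.

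**Second assumed child.** Feeding ends at 48 h, oxygen ends and vital signs are normal at 60 h, and discharge is at 72 h. Oxygen is given in a readmission from 336 to 384 h, and the next normal reading is at 396 h. The composite is 396 h as written and 60 h with the exclusion carried over, a shift of 336 h (14 days).

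**What triggers it.** The readmission must start more than 72 h after discharge and must involve oxygen, a low SpO2 reading, or an HR or RR reading marked abnormal. A late readmission for feeding or hydration alone, with normal vital signs, does not trigger it; there the exclusion works.

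**Group-level size (illustration only).** The SAP gives no rate of late readmission, so I assumed that 2%, 5% or 10% of children are pushed late. The 3-day median (72 h) is borrowed from Section 1.4, where it refers to symptom resolution. The distribution is log-logistic with scale 0.65. Section 1.4 writes the scale as 1/0.65, but its 95% probability of an effect in the right direction is approximated with σ = 0.65: Φ(|ln(2/3)| / √(6 × 0.65² / 48)) = 96.1%. With σ = 1/0.65 the same formula gives 77%. If a fraction p is moved beyond the quantile of interest, quantile F becomes 72 × [(F/(1 − p)) / (1 − F/(1 − p))]^0.65.

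| p | Median (h) | 75th percentile (h) |
|---|---|---|
| 0 | 72.0 | 147.0 |
| 2% | 73.9 | 155.2 |
| 5% | 77.1 | 170.0 |
| 10% | 83.2 | 205.0 |

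The median moves little at small p; most of the effect is in the upper tail.

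**The case against.** The strongest defence is that sustained normality is deliberate. Requiring a normal value with no later abnormal one is an ordinary definition of recovery, and the SAP uses the same form for undetectable virus in Table 16. This stands for the rule in general. It does not explain why one component of the same composite excludes late-readmission oxygen while another counts it.

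A reader might infer more: that letting HR and RR run to the end of follow-up is itself an error. After discharge these are measured "Once at clinic visits + Day 28" (Day 28 only if on site), so an HR marked abnormal on Day 14 and normal on Day 21 puts the event at (21 − 1) × 24 = 480 h. The documents do not support calling that a mistake. The 72 h limit is stated only for supplementation, and HR and RR normality is the investigator's judgement for the individual child. A child judged abnormal on Day 14 may well be one the endpoint means to count as not yet recovered.

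A reader might also infer that the added spread would mask a difference between arms. That is not shown. Section 5.3.2.3.2 plans only Kaplan-Meier summaries with confidence intervals for this endpoint; the AFT and MCP-Mod analyses there are for time to hospital discharge. The endpoint is not among the key endpoints of Section 5.6.

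There is partial mitigation. The oxygen exclusion still works in the stand-alone supplementation endpoints, and investigator-assessed clinical stability is analysed separately as a first event. Neither repairs this composite.

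**Conclusion.** The inconsistency stands, in a narrow form. In both versions of the composite, the oxygen component's late-readmission exclusion is cancelled by the SpO2 component, and no other text resolves it. For an affected child the shift is about two weeks (360 h and 336 h in the two assumed cases), or an event becomes a censoring.

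The group effect depends on how many children are readmitted late with oxygen or abnormal vital signs, which the SAP does not give. On borrowed inputs it is mainly an upper-tail effect. It is confined to a secondary, Cohort 1 only Kaplan-Meier summary and has no bearing on the primary test or the interim decision rules. The end-of-study horizon for HR and RR at clinic visits is a design choice and not part of the defect.

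**What to change.** Amend the composite in Table 20, for both the 92% and 95% versions:

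1. Within the composite, the SpO2 component disregards oxygen given in re-hospitalizations that began more than 72 h after first discharge, matching the oxygen component.
2. SpO2, HR and RR readings taken during those re-hospitalizations are also disregarded. Otherwise an abnormal reading from the same readmission would restore the override.
3. The sustained-normality rule stays for all other readings, including scheduled clinic visits.
4. The current unrestricted derivation is reported as a sensitivity analysis.

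A blanket 72 h cut-off for all vital-sign readings is not advised. For a discharge on Day 9 the window would end on Day 12, with no clinic visit between Days 8 and 14 (footnote to Table 6), so the sustained condition could be met with no scheduled check.

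The cost is a few lines of SAP text, one changed derivation and one extra Kaplan-Meier display per version. The downside is that a genuine late relapse no longer delays this endpoint, but it remains reported under re-hospitalization in the same section.

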The proportion (number [n] and percentage [%]) of subjects will be presented as frequency tabulation:

- Re-hospitalized (any reason): percentage (%) based on total number of hospitalized subjects in ITT-i analysis set and treatment group
- Re-hospitalized:
 - Adverse event:
 - Respiratory AEs:
 - ◆ RSV-related complications: modified definition as detailed in Section 5.4
 - ◆ Other respiratory AEs
 - Non-respiratory AEs
 - Other

In addition, the main reason(s) for re-hospitalization will be summarized descriptively.

Individual subject profiles will be provided for all subjects re-hospitalized.

Time to Discharge Since Hospital Admission, Time to Clinical Stability: Investigator Assessment Since Hospital Admission

These time to event variables will be analyzed using Kaplan-Meier analysis. Both the 80% and 95% 2-sided confidence intervals will be presented.

The aforementioned will be presented overall by treatment group and by the subgroups as defined in Section 2.4.

Need for ICU Stay, Need for Oxygen Supplementation, Requirement for Supplemental Feeding/Hydration

With reference to the definitions and derivations detailed in Section 5.3.1.3.2, summary includes those subjects not requiring the level of care/support at date/time of first dose of study drug.

The proportion (number [n] and percentage [%]) of subjects with data available will be presented, as frequency tabulation, by treatment group. Additionally, 95% 2-sided confidence interval for each binomial proportion within the individual categories will be presented as based on the Wilson score test.

Based on the categorization (Yes vs No), the difference in proportions between each active treatment group as compared to placebo will be investigated. Frequency procedure in SAS® provides Newcombe confidence limits with Mantel-Haenszel weights for the common risk difference (difference in proportion), controlling for the two randomization stratification factors (separately). The difference in proportion of 'Yes' for any ICU/supplementation need and both 80% and 95% 2-sided confidence intervals for this point estimate, controlling for randomization stratification factors (derived), will be presented.

Derived duration will be summarized descriptively only.

The aforementioned will be presented overall by treatment group and by the subgroups as defined in Section 2.4.

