RSV-related complications: modified definition	Any subject who experienced at least one emergent adverse event included in the list of complications below will receive code 1, subjects who did not experience any of the specified emergent adverse events will receive code 0.

Measurement	Formula
[study physician-identified complications]	
 Respiratory complications: respiratory failure, respiratory distress, apneic attacks, bronchiolitis, bronchial obstruction, pneumonia, asthmatic crisis. Infectious complications: otitis media, bacterial respiratory tract infections, sepsis; Cardiovascular complications: arrhythmia, cardiogenic shock, hemodynamic instability, congestive cardiac failure; Acid-base or electrolyte complications: metabolic acidosis (serum $\text{HCO}_3^- < 16$), metabolic alkalosis (serum $\text{HCO}_3^- > 30$) 
The final list of emergent adverse events to be considered as per modified definition of RSV-related complications, will be reviewed and documented prior to a database lock.
 
The modified definition for RSV-related complications will primarily be used as follows:
 
 from IA#3 and onwards in any decision rule that requires RSV-related complications data
Need for antibiotics related to complications associated with RSV: Investigator assessment [categorical]	
Need for antibiotics is defined as 'Yes' if the answers to the following 2 questions on the Adverse Events eCRF are answered with 'Yes' (Yes to both questions):
 
 Is this AE a complication related to the current respiratory infection? Concomitant or additional therapy given for this adverse event? 
And if the answer to the following question on the Concomitant Medications eCRF for the related medication is answered with 'Yes'.
 
 Was this medication an Antibiotic?

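### The re-hospitalization breakdown nests all modified-definition RSV-related complications under respiratory adverse events, although that definition includes non-respiratory categories

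*SAP*

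**What the plan says.** Table 20 in SAP Section 5.3.1.3.2 defines the need for re-hospitalization in Cohort 1. The reason is recorded as adverse event or other. For the first of these, the table continues: "If reason for re-hospitalization is indicated as AE, further differentiation will be made as follows". There are then two headings, *Respiratory AEs* and *Non-respiratory AEs*. The first entry under the respiratory heading is "RSV-related complications: modified definition as detailed in Section 5.4", and the second is the remainder, "Other respiratory AEs".

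Section 5.3.2.3.2 (RSV-related Re-hospitalization) repeats the hierarchy for the frequency table. The indentation there is clear: the complications and the other respiratory events are both children of the respiratory heading, and the non-respiratory heading is its sibling.

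The modified definition is in Table 22 of Section 5.4.1. It works across all its categories: "Any subject who experienced at least one emergent adverse event included in the list of complications below will receive code 1". After a respiratory category come three more:

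- the second category, given as "Infectious complications: otitis media, bacterial respiratory tract infections, sepsis"
- the third category, given as "Cardiovascular complications: arrhythmia, cardiogenic shock, hemodynamic instability, congestive cardiac failure"
- the fourth category, which opens "Acid-base or electrolyte complications: metabolic acidosis" and has metabolic alkalosis as its other term

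The term list is not yet closed. The SAP leaves its final review and documentation until shortly before the database is locked.

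**The concern.** A split of re-admissions into respiratory and non-respiratory exists to show cause. Here the respiratory branch imports a definition that is wider than the branch. A programmer who follows the text would flag every re-admission for an event on the modified list and report it as respiratory, including sepsis, heart failure or an arrhythmia. The non-respiratory row would then hold only non-respiratory events that are not on the list.

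At stake is the cause-specific reading of a listed secondary endpoint, since Section 5 names the need for (re)hospitalization among the clinical course endpoints. The respiratory row would be too high and the non-respiratory row too low by the number of such re-admissions.

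**Working it through.** The SAP gives no figure to reproduce. The check sets the hierarchy beside the definition it cites and counts terms.

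**Step 1: is the nesting real?** The bullets in Table 20 could have lost their indentation in the PDF. The same list in Section 5.3.2.3.2 kept it and shows the complications under the respiratory heading. The word *Other* in the sibling entry also implies that the entry before it is respiratory. So the nesting belongs to the plan.

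**Step 2: what does the cited definition contain?** Terms listed in Table 22:

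| Category | Terms | Not respiratory |
|---|---|---|
| Respiratory | 7 | 0 |
| Infectious | 3 | 2 (sepsis, otitis media), or 1 if otitis media is taken as respiratory |
| Cardiovascular | 4 | 4 |
| Acid-base or electrolyte | 2 | 2 |
| Total | 7 + 3 + 4 + 2 = 16 | 0 + 2 + 4 + 2 = 8, or 0 + 1 + 4 + 2 = 7 |

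Bacterial respiratory tract infections, the third infectious term, count as respiratory. The range of 7 to 8 reflects otitis media alone.

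**Step 3: is the reference restricted anywhere?** Neither Section 5.3.1.3.2 nor Section 5.3.2.3.2 limits it to the respiratory category. Table 22 also gives the protocol (investigator-assessed) definition, which has a separate subcategory for infectious complications that are not respiratory. The SAP itself therefore recognises that an RSV-related complication need not be respiratory.

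**Step 4: where does each event go?**

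| Re-admission for | On the modified list? | Reading A: everything on the list goes in the complications row | Reading B: sort by respiratory first, then by list |
|---|---|---|---|
| Bronchiolitis | Yes | Respiratory, complication | Respiratory, complication |
| Sepsis | Yes | Respiratory, complication | Non-respiratory |
| Arrhythmia | Yes | Respiratory, complication | Non-respiratory |
| Congestive cardiac failure | Yes | Respiratory, complication | Non-respiratory |
| Metabolic acidosis | Yes | Respiratory, complication | Non-respiratory |

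Reading A mislabels the last four. Reading B labels them correctly by organ system, but the row named for the modified definition then omits subjects who meet it. The readings differ for every listed event that is not respiratory, so two programmers could produce different tables from the same data.

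**Step 5: size per subject.** The target is 48 subjects per arm in Cohort 1. If the sub-rows use the denominator stated for the any-reason row (hospitalized ITT-i subjects in the arm), one misplaced subject moves about 100/48 = 2.1 percentage points from one row to the other. The ITT-i denominator may be smaller than 48, and the figure then slightly larger. The SAP gives no re-admission rate or distribution of causes, so the number of such subjects cannot be estimated.

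**The case against.** The strongest reply is that the heading governs. Read from the top, an event is first judged respiratory or not, and only respiratory events are then divided into those on the modified list and the rest. An arrhythmia would then go to the non-respiratory row. This reading is possible, but the text does not state it, and it leaves the mismatch between the row's name and its content shown above. It does mean that misclassification is the natural outcome and not a certain one.

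The second reply is that little depends on the table, and this stands. Section 5.3.2.3.2 makes it a frequency tabulation with no test or interval, and adds a descriptive summary of the main reasons and individual profiles for all re-hospitalized subjects. Section 5.4.2 tabulates modified-definition complications by preferred term within subcategory. Section 6.1.3 summarises adverse events by body system and preferred term. Re-hospitalization is not a key clinical course endpoint in Section 3, nor part of the decision rules in Section 5.6.

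Two stronger inferences should be resisted:

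- **A hidden cardiac signal.** A reader might infer that the table could conceal QT-related events. Section 6.1.3 identifies those by preferred term, independently of this table, and also lists all adverse events. Most of the terms in Table 24, such as QT prolongation, syncope and cardiac arrest, are not named in the modified definition. The evident overlap is through the term arrhythmia.
- **A reversed comparison between arms.** A reader might infer that one or two cases could reverse the respiratory versus non-respiratory split by arm. With no re-admission rate in the SAP, nothing supports that.

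The count of 7 or 8 in 16 describes a list that is still to be finalised. It is not an expected share of events. Finalising the terms would not cure the problem, because the four categories are already written into the SAP.

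**Conclusion.** The concern holds as an inconsistency between a table's heading and the definition placed beneath it, present in both Section 5.3.1.3.2 and Section 5.3.2.3.2. Three of the four categories in the modified definition are not headed respiratory. Under the natural reading, re-admissions for the non-respiratory terms are reported as respiratory and are missing from the non-respiratory row. Under the alternative reading, the complications row is incomplete against its own label.

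The consequence is limited to those rows of one descriptive table. The any-reason row, the split between adverse event and other, the primary endpoint, the interim rules and the safety outputs do not change. The conclusion rests on the four categories in Table 22 remaining when the term list is finalised, and on no restriction being stated outside the SAP. It is still worth correcting, because the split has no purpose other than to show cause and the correction is cheap.

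**What to change.** Make the same change in Table 20 (Section 5.3.1.3.2) and in the re-hospitalization list of Section 5.3.2.3.2. Either of two forms works:

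1. Under adverse event, make RSV-related complication (modified definition) a level of its own, beside other respiratory events and other non-respiratory events. Showing its four categories is optional, since Section 5.4.2 already tabulates the subcategories.
2. Keep the present two headings, limit the complications entry under the respiratory one to the respiratory category plus bacterial respiratory tract infections, and place the remaining complications under the non-respiratory heading. State where otitis media belongs.

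The cost is a few lines of SAP text and one table shell. The change needs no new data and no change to any other analysis, and it can be settled together with the final term list before database lock.
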